12.3. Data Analyses

Presentation of summary statistics for continuous variables will include N, mean, median, standard deviation, minimum, and maximum values for non-missing data. For categorical variables, the number and percentage under each category for non-missing data will be presented.

Additionally, subjects meeting this study's eligibility criteria under the PFD Registry may be included in the analyses plan. The intention is to utilize a shared control arm from the PFD Registry.

12.3.1. Rate of Office-Based Intervention for Recurrence

Statistical testing will be performed to determine if the rate of office-based intervention for recurrence in the treatment group will be superior to the control group. The null hypothesis is that the rate of office-based intervention for recurrence in treatment group is greater than or equal to the rate in control group:

$$H_0: \pi_{treatment} - \pi_{control} \geq 0$$

The alternative hypothesis is:

$$H_a: \pi_{treatment} - \pi_{control} < 0$$

where $\pi_{treatment}$ and $\pi_{control}$ are the office-based intervention rates for recurrence in treatment group and control group respectively. The rejection of null hypothesis indicates the superiority of the treatment group over the control group.

12.3.2. Rate of Surgical Intervention for Recurrence

Statistical testing will be performed to determine if the rate of surgical intervention for recurrence in treatment group will be superior to the control group. The null hypothesis is that the rate of surgical intervention for recurrence in treatment group is greater than or equal to the rate in control group:

$$H_0: \pi_{treatment} - \pi_{control} \geq 0$$

The alternative hypothesis is:

$$H_a: \pi_{treatment} - \pi_{control} < 0$$

where $\pi_{treatment}$ and $\pi_{control}$ are the surgical intervention rates for recurrence in treatment group and control group respectively. The rejection of null hypothesis indicates the superiority of the treatment group over the control group.

The propensity score adjusted analysis described in Section 12.2.3 (Propensity Score Methodology) will be used for testing the null hypothesis and computing the confidence intervals for rate of office-based intervention for recurrence and surgical intervention for recurrence between treatment group and control group.

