12.1.2.1. Hypotheses

Statistical testing will be performed to determine if the de novo dyspareunia rate of treatment group is non-inferior to the control group. The null hypothesis is that the de novo dyspareunia rate in treatment group is greater than or equal to the rate in control group plus margin:

$$H_0: \pi_{treatment} - \pi_{control} \geq \Delta$$

The alternative hypothesis is:

$$H_a: \pi_{treatment} - \pi_{control} < \Delta$$

where $\pi_{treatment}$ and $\pi_{control}$ are the de novo dyspareunia rate in treatment group and control group respectively, and $\Delta > 0$ is defined as the non-inferiority margin.

Statistical testing will be performed to determine if the AE incidences (pelvic pain, infection, vaginal shortening, atypical vaginal discharge, neuromuscular problems, vaginal scarring, de novo vaginal bleeding, fistula formation and/or de novo voiding dysfunction) rate of treatment group is non-inferior to the control group. The null hypothesis is that the AE incidences rate in treatment group is greater than or equal to the rate in control group plus margin:

$$H_0: \pi_{treatment} - \pi_{control} \geq \Delta$$

The alternative hypothesis is:

$$H_a: \pi_{treatment} - \pi_{control} < \Delta$$

where $\pi_{treatment}$ and $\pi_{control}$ are the AE incidence rates in treatment group and control group respectively, and $\Delta > 0$ is defined as the non-inferiority margin.

The propensity score adjusted confidence intervals described in Section 12.2.3 (Propensity Score Methodology) will be used to summarize the mean score improvement of Quality of Life (PFIQ, PFDI, PISQ, TOMUS pain scale) of the Xenform (treatment) group compared to that of the native tissue repair (control) group.

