12.1.2.2. Sample Size

The rate of de novo dyspareunia is anticipated to be approximately 9%.¹⁷ With type I error of 0.05 and type II error of 0.20 (power 80%), 326 subjects (163 subjects per arm) are needed to detect non-inferiority with a margin of 7.9%.

The rate of AE incidence (pelvic pain, infection, vaginal shortening, atypical vaginal discharge, neuromuscular problems, vaginal scarring, de novo vaginal bleeding, fistula formation and/or de novo voiding dysfunction) is anticipated to be approximately 12%.¹⁵⁻¹⁸ With type I error of 0.05 and type II error of 0.20 (power 80%), 330 subjects (165 subjects per arm) are needed to detect non-inferiority with a margin of 8.9%.

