12.3.3. Rate of Office-Based Intervention for Complications

Statistical testing will be performed to determine if the rate of office-based intervention for complications in the mesh (treatment) group is non-inferior to the native tissue repair (control) group. The null hypothesis is that the rate of office-based intervention for complications in treatment group is greater than or equal to the rate in control group plus margin:

$$H_0: \pi_{treatment} - \pi_{control} \geq \Delta$$

The alternative hypothesis is:

$$H_a: \pi_{treatment} - \pi_{control} < \Delta$$

where $\pi_{treatment}$ and $\pi_{control}$ are the office-based intervention rates for complication in treatment group and control group respectively, and $\Delta > 0$ is defined as the non-inferiority margin.

The rate of office-based intervention for complication is anticipated to be approximately 2%. With type I error of 0.025 and type II error of 0.10 (power 90%), 330 subjects (165 subjects per arm) are needed to detect non-inferiority with a margin of 5%.

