12.3.4. Rate of Surgical Intervention for Complications

Statistical testing will be performed to determine if the rate of surgical intervention for complications of the mesh (treatment) group is non-inferior to the native tissue repair (control) group. The null hypothesis is that the rate of surgical intervention for complications in treatment group is greater than or equal to the rate in control group plus margin:

$$H_0: \pi_{treatment} - \pi_{control} \geq \Delta$$

The alternative hypothesis is:

$$H_a: \pi_{treatment} - \pi_{control} < \Delta$$

where $\pi_{treatment}$ and $\pi_{control}$ are the probabilities of having surgical intervention for complication in treatment group and control group respectively, and $\Delta > 0$ is defined as the non-inferiority margin.

The rate of surgical intervention complication is anticipated to be approximately 1%. With type I error of 0.025 and type II error of 0.10 (power 90%), 260 subjects (130 subjects per arm) are needed to detect non-inferiority with a margin of 4%.

The propensity score adjusted analysis described in Section 12.2.3 (Propensity Score Methodology) will be used for testing the null hypothesis and computing the confidence intervals for rate office-based intervention for complication and surgical intervention for complication between treatment group and control group.

For each group, logistic regression will be performed, to include office-based intervention for recurrence as a covariate for analyzing the primary endpoint (success rate of improvement in pelvic organ prolapse at 36 months) data.

For each group, Cox regression will be performed, to include surgical intervention for recurrent prolapse as a covariate for analyzing adverse events (pelvic pain, infection, vaginal shortening, vaginal scarring, de novo vaginal bleeding, fistula formation and/or de novo voiding dysfunction) data.

Descriptive statistics for the baseline characteristics and QOL outcome for the non-surgery (i.e. pessary) group will be summarized from the AUGS PFD Registry Level 1/2 database.

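### Six further 36-month between-arm tests have no gate, order or adjustment, and the two superiority tests have no stated significance level

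*Combined protocol and SAP*

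**What the plan says.** Section 12.1.1 defines the two co-primary tests, composite success and serious related complications, each judged with a two-sided 90% confidence interval. The same document then sets out six more between-arm tests, each with a written null and alternative.

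- **De novo dyspareunia, non-inferiority** (12.1.2.1): "Statistical testing will be performed to determine if the de novo dyspareunia rate of treatment group is non-inferior to the control group". Section 12.1.2.2 sizes it: "With type I error of 0.05 and type II error of 0.20 (power 80%), 326 subjects (163 subjects per arm) are needed", for a 9% rate and a 7.9% margin.
- **Incidence of the listed adverse events, non-inferiority** (12.1.2.1). Section 12.1.2.2: "With type I error of 0.05 and type II error of 0.20 (power 80%), 330 subjects (165 subjects per arm) are needed", for a 12% rate and an 8.9% margin.
- **Office-based intervention for complications, non-inferiority** (12.3.3): "With type I error of 0.025 and type II error of 0.10 (power 90%), 330 subjects (165 subjects per arm) are needed", for a 2% rate and a 5% margin.
- **Surgical intervention for complications, non-inferiority** (12.3.4): "With type I error of 0.025 and type II error of 0.10 (power 90%), 260 subjects (130 subjects per arm) are needed", for a 1% rate and a 4% margin.
- **Office-based intervention for recurrence, superiority** (12.3.1): "Statistical testing will be performed to determine if the rate of office-based intervention for recurrence in the treatment group will be superior to the control". No alpha, power or sample size is given.
- **Surgical intervention for recurrence, superiority** (12.3.2). Again no alpha, power or sample size is given.

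Both superiority sections state the claim that follows: "The rejection of null hypothesis indicates the superiority of the treatment group over the control group". Section 12.3.2 sends the test and its interval to the propensity-score method of 12.2.3, which names no level. The only sequential rule in the document is in 12.3.8.1, where superiority on the composite at 12 months is tested only after non-inferiority has been shown.

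**The concern.** Requiring both co-primaries to succeed does not inflate their error. The six further tests are different, because each can produce a favourable statement about the graft alone. The plan does not tie them to the co-primaries, rank them, share alpha among them or say that they are only supportive. Read literally, superiority on re-surgery for recurrence could be declared after the effectiveness or safety co-primary had failed.

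The missing level is a separate defect that needs no error-rate calculation. The document uses one-sided 0.05 for the co-primaries, 0.025 for the complication interventions, and a 95% interval for the interim descriptive comparison. A one-sided p-value between 0.025 and 0.05 on either superiority test could therefore be called superiority or not, and the choice could be made with the result in view.

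**Working it through.** **Step 1. Are the stated alphas one-sided or two-sided?** Rates, margins, alphas and powers come from 12.1.2.2, 12.3.3 and 12.3.4. With equal true rates and unpooled variance, n per arm = (z₁₋α + z₁₋β)² × 2p(1−p) / Δ². Taking alpha as one-sided:

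- Dyspareunia: 6.183 × 0.1638 / 0.079² = 162.3 (plan: 163)
- Adverse-event incidence: 6.183 × 0.2112 / 0.089² = 164.8 (plan: 165)
- Office-based, complications: 10.507 × 0.0392 / 0.05² = 164.8 (plan: 165)
- Surgical, complications: 10.507 × 0.0198 / 0.04² = 130.0 (plan: 130)

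All four agree with the plan to rounding. Taking alpha as two-sided gives 207, 210, 195 and 154, which do not. The stated levels are therefore one-sided, per-test and unadjusted: 0.05, 0.05, 0.025 and 0.025.

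**Step 2. Independent tests, every null at its boundary** (non-inferiority at the margin, superiority at zero difference). The chance of at least one false rejection is 1 − Π(1 − αₖ).

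- Four tests with a stated alpha: 1 − 0.95² × 0.975² = 14.2%
- All six, superiority at an assumed 0.025: 1 − 0.95² × 0.975⁴ = 18.4%
- All six, superiority at an assumed 0.05: 1 − 0.95⁴ × 0.975² = 22.6%

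The sums of the alphas, 15%, 20% and 25%, are upper bounds under any dependence.

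**Step 3. Positive correlation.** The outcomes come from the same women, so some positive correlation is plausible, but the documents give no value. With equally correlated normal test statistics, the probability is 1 − ∫ φ(u) Π Φ((z₁₋αₖ − √ρ·u) / √(1−ρ)) du.

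| Set of tests | ρ = 0 | ρ = 0.5 | ρ = 0.9 |
|---|---|---|---|
| Four with a stated alpha | 14.2% | 11.4% | 7.2% |
| Six, superiority at 0.025 | 18.4% | 13.5% | 7.6% |
| Six, superiority at 0.05 | 22.6% | 16.2% | 9.0% |

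**Step 4. The superiority pair alone.** At 0.025 each the sum is 5%, so the pair stays at or below 5% whatever the correlation (1 − 0.975² = 4.9% if independent). At 0.05 each, independence gives 1 − 0.95² = 9.8%.

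**Step 5. What a full six-step order would cost.** Suppose both co-primaries and then all four non-inferiority tests had to succeed before the first superiority test. Assume the plan's rates hold, the arms are equal and the tests are independent.

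- With 181 per arm throughout, the powers are 0.801, 0.938, 0.837, 0.832, 0.925 and 0.969. Their product is about 47%.
- With 227 per arm for every test except effectiveness, they are 0.801, 0.972, 0.903, 0.898, 0.967 and 0.990. Their product is about 60%.

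**The case against.** The strongest reply is that the plan already shows which tests matter. The synopsis lists only the two co-primaries as the primary hypothesis. The other tests sit under secondary endpoints or general data analyses, and nothing ties study success to them. Several are safety comparisons, and making those wait on an effectiveness result is a design preference. This has force for the four non-inferiority tests, which can reasonably be reported as supportive. It does not answer the superiority tests, because 12.3.1 and 12.3.2 themselves say that rejection establishes superiority.

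Five stronger readings are tempting, and the documents do not support them:

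- **A single family-wise figure such as 16%.** That needs a correlation of 0.5 and superiority at 0.05. The documents state neither.
- **All six tests run at the full 0.05.** Two are stated at 0.025 and two have no level.
- **A stated 5% family-wise rate is exceeded by a fixed multiple.** The 0.05 is a per-test level, and the documents give no family-wise rate.
- **The four intervention tests have no endpoint status.** Secondary endpoint 6 covers absence of re-intervention or re-surgery for recurrence, persistence or graft exposure/erosion. Section 11.5 announces comparisons of office-based and surgical interventions, and 12.1.2.3 lists re-treatment among the secondary analyses. What is missing is their place in a testing scheme.
- **The co-primary conclusions are compromised.** They are not.

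The count of six is also a reading. It treats the adverse-event list as one combined rate and leaves out the 12-month tests in 12.3.8.1.

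**Conclusion.** The concern holds. Six 36-month tests are unadjusted, unordered and not conditional on the co-primaries, and the two that lead to a superiority statement have no significance level.

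The chance of at least one false claim is 14.2% for the four tests with a stated alpha. It is 18.4% to 22.6% for all six, depending on the superiority level (assumed 0.025 to 0.05). These figures assume independence and every null at its boundary. An assumed common correlation of 0.9 lowers the six-test figure to 7.6% to 9.0%, which is still above 5%. The size is therefore best given as a range.

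The defect affects secondary claims only. The type I error of the co-primary tests does not change.

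**What to change.** Add to 12.1.2.1 and 12.3 that:

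- a formal claim from these tests is made only if both 36-month co-primaries are met;
- the two superiority tests each use one-sided 0.025, with a two-sided 95% interval, which keeps that pair at or below 5%;
- the four non-inferiority tests are reported at their stated alphas as supportive, with intervals and no formal claim.

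If the sponsor also wants formal claims on the four non-inferiority tests, it should fix a testing order. That order must be chosen without reference to the by-arm 12-month interim, since 12.3.8 allows the interim to cover some or all secondary endpoints. Putting all four ahead of superiority leaves only about a 47% to 60% chance of reaching the first superiority test, under the assumptions of Step 5.

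The simpler alternative is to replace the superiority sentences in 12.3.1 and 12.3.2 with: *exploratory; interval reported without a claim*.

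Either route changes wording only. No subjects or data are added, and the stated alphas and sample sizes stay. The cost is that no formal claim can be made after a failed co-primary, or from any test labelled supportive or exploratory.

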12.3.3. Rate of Office-Based Intervention for Complications

Statistical testing will be performed to determine if the rate of office-based intervention for complications in the mesh (treatment) group is non-inferior to the native tissue repair (control) group. The null hypothesis is that the rate of office-based intervention for complications in treatment group is greater than or equal to the rate in control group plus margin:

$$H_0: \pi_{treatment} - \pi_{control} \geq \Delta$$

The alternative hypothesis is:

$$H_a: \pi_{treatment} - \pi_{control} < \Delta$$

where $\pi_{treatment}$ and $\pi_{control}$ are the office-based intervention rates for complication in treatment group and control group respectively, and $\Delta > 0$ is defined as the non-inferiority margin.

The rate of office-based intervention for complication is anticipated to be approximately 2%. With type I error of 0.025 and type II error of 0.10 (power 90%), 330 subjects (165 subjects per arm) are needed to detect non-inferiority with a margin of 5%.

12.3.4. Rate of Surgical Intervention for Complications

Statistical testing will be performed to determine if the rate of surgical intervention for complications of the mesh (treatment) group is non-inferior to the native tissue repair (control) group. The null hypothesis is that the rate of surgical intervention for complications in treatment group is greater than or equal to the rate in control group plus margin:

$$H_0: \pi_{treatment} - \pi_{control} \geq \Delta$$

The alternative hypothesis is:

$$H_a: \pi_{treatment} - \pi_{control} < \Delta$$

where $\pi_{treatment}$ and $\pi_{control}$ are the probabilities of having surgical intervention for complication in treatment group and control group respectively, and $\Delta > 0$ is defined as the non-inferiority margin.

The rate of surgical intervention complication is anticipated to be approximately 1%. With type I error of 0.025 and type II error of 0.10 (power 90%), 260 subjects (130 subjects per arm) are needed to detect non-inferiority with a margin of 4%.

The propensity score adjusted analysis described in Section 12.2.3 (Propensity Score Methodology) will be used for testing the null hypothesis and computing the confidence intervals for rate office-based intervention for complication and surgical intervention for complication between treatment group and control group.

For each group, logistic regression will be performed, to include office-based intervention for recurrence as a covariate for analyzing the primary endpoint (success rate of improvement in pelvic organ prolapse at 36 months) data.

For each group, Cox regression will be performed, to include surgical intervention for recurrent prolapse as a covariate for analyzing adverse events (pelvic pain, infection, vaginal shortening, vaginal scarring, de novo vaginal bleeding, fistula formation and/or de novo voiding dysfunction) data.

Descriptive statistics for the baseline characteristics and QOL outcome for the non-surgery (i.e. pessary) group will be summarized from the AUGS PFD Registry Level 1/2 database.

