12.1.1.2. Sample Size

The statistical power calculation is based on a non-inferiority assumption with a binary primary outcome. Objective success, based on a composite endpoint of anatomic and symptomatic success at 36 month is assumed to be 70.0%^{5-8, 16} for the native tissue arm. With type I error of 0.05 and type II error of 0.20 (power 80%), 362 subjects (181 subjects per arm) are needed to detect non-inferiority of transvaginal biologic to native tissue repair, using a margin of 12.0%.

To assess for safety, the overall complication rate (i.e., serious device-related or serious procedure-related adverse events) is anticipated to be approximately 14% per arm.⁹ With type I error of 0.05 and type II error of 0.10 (power 90%), 308 subjects (154 subjects per arm) are needed to detect non-inferiority with a margin of 11.6%.

To assess for office-based interventions for complications, the rate is anticipated to be approximately 2%.⁹ With type I error of 0.025 and type II error of 0.10 (power 90%), 330 subjects (165 subjects per arm) are needed to detect non-inferiority with a margin of 5%.

To assess for of surgical intervention for complications, the rate is anticipated to be approximately 1%.⁹ With type I error of 0.025 and type II error of 0.10 (power 90%), 260 subjects (130 subjects per arm) are needed to detect non-inferiority with a margin of 4%.

Non-surgical subjects will not be enrolled into this clinical study as all data on this cohort of subjects will be obtained from the AUGS Pelvic Floor Disorders Registry under Level 2 and analyzed with data from this clinical study.

Using the above calculations and assuming a 20% loss to follow-up rate, a total of 454 subjects (227 per study arm) will be enrolled to achieve the primary endpoint of success at 36 months.

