12.1.1.3. Statistical Methods

For the primary effectiveness endpoint, non-inferiority will be evaluated using a two-sided 90% confidence interval for the treatment difference (Xenform minus native tissue repair). If the entire confidence interval is above the margin (i.e., -12%), non-inferiority will be demonstrated. The confidence interval will be calculated based on the pooling of treatment differences across propensity score strata for a binary endpoint, as described in Section 12.2.3 (Propensity Score Methodology).

If any data on the primary efficacy endpoint is missing, multiple imputation will be performed in which the missing values will be imputed five times under a logistic distribution model, using a fully conditional specification that includes the treatment arm and the assessments of the treatment success endpoint at each of 2, 6, 12, 18, and 24 months. As

a sensitivity analysis, the comparison of treatments will also be performed using the following methods:

- Tipping point analysis
- Available cases only (i.e., only the subjects for whom the endpoint was assessed)

For the primary safety endpoint, the proportions will be calculated using for the numerator the number of subjects with an endpoint event and for the denominator the number of subjects in the analysis population (ITT and Per Protocol group). Non-inferiority will be evaluated using a two-sided 90% confidence interval for the treatment difference (Xenform minus native tissue repair). If the entire confidence interval is below the margin (i.e., 11.6%), non-inferiority will be demonstrated. The confidence interval will be calculated based on the pooling of treatment differences across propensity score strata for a binary endpoint, as described in Section 12.2.3 (Propensity Score Methodology).

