12.2.3. Propensity Score Methodology

Analyses comparing the treatment groups will be adjusted for the propensity score. The propensity score is the probability that the subject enrolled in the mesh arm rather than the native tissue (control) arm, given the characteristics of the subject and center. The characteristics identified are as follows: age, race, body mass index, smoking, diabetes, post-menopausal, prior prolapse repair, prior hysterectomy, estrogen use, POP-Q C measurement, POP-Q Ba measurement, POP-Q Bp measurement, concomitant repair for stress urinary incontinence, and surgeon case volume. Logistic regression of both treatment arms (i.e., (transvaginal biologic mesh repair vs. native tissue repair) on these characteristics will be used to estimate the propensity score. The subjects will then be partitioned into five strata corresponding to quintiles of the propensity score. If the balance between treatment arms within the strata is deemed adequate, the treatment difference adjusted for propensity score stratum will be estimated as described in the following.

The propensity adjusted treatment difference will be based on averaging the treatment differences of the propensity score strata. For a binary outcome, the within-stratum treatment difference is $D_j = p_{T_j} - p_{C_j}$, where p_{T_j} and p_{C_j} is the proportion of treatment and control subjects, respectively, in stratum j . The variance of D_j is approximately

$$V_j = \frac{p_{T_j}(1 - p_{T_j})}{n_{T_j}} + \frac{p_{C_j}(1 - p_{C_j})}{n_{C_j}}$$

Denoting the number of subjects in stratum j by $n_j = n_{T_j} + n_{C_j}$, the treatment difference will be estimated by the (weighted) mean of the within-stratum treatment differences

$$D = \sum_j \frac{n_j}{n} D_j$$

where $n = \sum_j n_j$ is the total sample size across all strata and study arms. D is approximately normally distributed with variance

$$V = \sum_j \left(\frac{n_j}{n}\right)^2 V_j$$

from which a confidence interval for the true treatment difference will be constructed. For each continuous outcome, the confidence interval will be constructed similarly, with D and V obtained as above with the treatment difference within each stratum replaced by $D_j = \bar{X}_{T_j} - \bar{X}_{C_j}$, where \bar{X}_{T_j} and \bar{X}_{C_j} , respectively, is the mean of the treatment and control subjects, and

$$V_j = \frac{S_{T_j}^2}{n_{T_j}} + \frac{S_{C_j}^2}{n_{C_j}}$$

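### The unpooled Wald interval planned for the two complication-intervention non-inferiority tests runs at about 3.5–5.1% one-sided error instead of the declared 2.5%, and a score test that holds 2.5% lacks the stated 90% power at 165 and 130 per arm

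*Combined protocol and SAP*

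**What the plan says.** Section 12.3.3 tests whether office-based intervention for complications is non-inferior under Xenform. The anticipated rate is 2% and the margin 5 percentage points: "With type I error of 0.025 and type II error of 0.10 (power 90%), 330 subjects (165 subjects per arm) are needed". Section 12.3.4 does the same for surgical intervention, with a 1% rate, a 4-point margin, the same error and power, and 130 per arm. The synopsis and 12.1.1.2 repeat both sets of figures.

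The last part of 12.3.4 assigns the analysis of both endpoints to the propensity score method of 12.2.3, which "will be used for testing the null hypothesis and computing the confidence intervals for rate office-based intervention for complication and surgical intervention for complication". Section 12.2.3 takes the risk difference in each of five propensity quintiles, gives it the variance p_T(1−p_T)/n_T + p_C(1−p_C)/n_C from observed proportions, and averages with weights n_j/n. It treats the result as normal, "from which a confidence interval for the true treatment difference will be constructed". No score or exact method, small-count correction or zero-cell rule is given.

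None of 12.2.3, 12.3.3 and 12.3.4 states a confidence level. For the two primary endpoints, 12.1.1.3 says "non-inferiority will be evaluated using a two-sided 90% confidence interval for the treatment difference (Xenform minus native tissue repair"). On enrolment, 12.1.1.2 says "assuming a 20% loss to follow-up rate, a total of 454 subjects (227 per study arm) will be enrolled".

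**The concern.** An unpooled Wald interval is unreliable when few events are expected. At a 1% rate and 227 per arm, one arm has about 2.3 expected events in total, or about 0.45 per quintile. An arm with no events in a stratum adds nothing to the variance. The standard error is then too small, the upper limit too low, and non-inferiority is declared too often. That error favours the device.

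The sample sizes come from the same variance formula. The question is therefore whether 165 and 130 per arm deliver both properties claimed for them, 0.025 and 90%. At stake is the validity of two formal safety claims that have their own hypotheses, margins and sample-size statements.

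**Working it through.** **Inputs.** Rates p = 2% and 1%, margins d = 5 and 4 points, error 0.025, power 90%, and 165 and 130 per arm (12.3.3, 12.3.4). Arms of 181 and 227 come from 12.1.1.2. The 0.025 is read as one-sided, because only that reading reproduces the stated sizes; one-sided 0.05 would give 135 and 106.

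**1. The plan's own figures.** n per arm = (1.96 + 1.2816)² × 2p(1−p)/d².

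- Office: 10.507 × 0.0392 / 0.0025 = 164.8, so 165.
- Surgical: 10.507 × 0.0198 / 0.0016 = 130.03; the plan states 130.

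Both are right for this formula.

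**2. Actual error and power, no strata.** All pairs of binomial counts were enumerated. The Wald test rejects when D + 1.96√V < d. The comparison is a score test (Miettinen-Nurminen or Farrington-Manning; they agree here), whose variance is computed under the constraint that the difference equals the margin. Error is taken at control = p and treatment = p + d (2% vs 7%; 1% vs 5%), and power at equal rates.

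| Test | n per arm | Wald error | Wald power | Score error | Score power |
|---|---|---|---|---|---|
| Office | 165 | 4.1% | 89.8% | 1.9% | 75.0% |
| Office | 181 | 3.8% | 91.3% | 2.1% | 81.1% |
| Office | 227 | 3.5% | 95.2% | 2.1% | 90.3% |
| Surgical | 130 | 5.0% | 87.2% | 1.5% | 56.7% |
| Surgical | 181 | 4.3% | 93.3% | 1.8% | 82.5% |
| Surgical | 227 | 4.4% | 97.5% | 1.9% | 90.4% |

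An illustration for the surgical endpoint at 227 per arm, with one event in control: the Wald rule declares non-inferiority with up to 5 Xenform events, since 4/227 + 1.96 × 0.0107 = 0.0386 < 0.04. The score rule allows at most 3.

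**3. Five equal strata with the 12.2.3 weights, arms balanced in each (simulation, 200,000 runs).** Wald error is 4.1%, 4.0% and 3.7% (office; 165, 181, 227) and 5.1%, 4.6% and 4.2% (surgical; 130, 181, 227). Score power at the stated sizes is 77% and 59%. Stratification with balanced arms is therefore not the cause.

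**4. Other control rates.** At 227 per arm without strata:

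| True control rate | Wald error, office | Wald error, surgical |
|---|---|---|
| 0.5% | 4.4% | 5.2% |
| 1% | 4.0% | 4.4% |
| 2% | 3.5% | 3.5% |
| 3% | 3.2% | 3.3% |
| 4% | 3.1% | 3.1% |

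Every value exceeds 2.5%.

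**5. Unbalanced strata.** The documents give no treated shares, so these are assumptions. At 181 per arm, shares running over the quintiles from 40 to 60%, 30 to 70% and 20 to 80% give Wald error of 4.1%, 4.3% and 4.9% (office) and 5.1%, 5.5% and 6.6% (surgical). With shares of 20–80%, score power is 69–70% at 181 and 80–81% at 227.

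**6. If the two-sided 90% level of 12.1.1.3 were carried over.** With 1.645 in place of 1.96, the error is 6.4–6.6% (office) and 6.8–7.1% (surgical).

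**The case against.** The strongest reply is that 165 and 130 are endpoint-specific minimums, not the trial's size. With 227 per arm planned, a score test has about 90% power for both endpoints, and enrolment closed in December 2016 according to the timeline in 10.1, so rewording these statements alters no design decision. That is right about power, and it makes the remedy affordable. It does not remove the excess error, which at 181–227 per arm with balanced arms is 3.5–4.0% (office) and 4.2–4.6% (surgical). The twofold figure applies only at 130 per arm.

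A second reply is that the planned Wald test does have nearly 90% power at the stated sizes, and that part of the score test's shortfall comes from its own conservatism. Both statements are true. However, raising the Wald critical value until its error is at most 2.5% at the anticipated control rate leaves 84% power at 165 and 71% at 130. Holding 0.025 therefore costs power under either approach.

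Third, the 90% interval is tied to the primary endpoints, whose stated error of 0.05 it matches, and nothing sends these tests there. The result in step 6 is accordingly a risk from silence, not the plan's rule. Similarly, 12.2.1 places secondary endpoints on ITT, which partly covers the denominator, although the counting rule in 12.1.1.3 is written for the primary safety endpoint only. Section 12.2.3 also makes the stratified estimate conditional on adequate balance, which may or may not limit the imbalance assumed in step 5. Taken alone, the level and the denominator would be missing detail.

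**Conclusion.** The concern holds. The interval in 12.2.3 does not deliver the declared 0.025 for these two tests: with balanced arms its one-sided error is about 3.5–5.1%, or 1.4 to 2 times the target. The sample sizes are arithmetically correct, but for a test that does not hold its level. A test that does has 75–77% power at 165 (office) and 57–59% at 130 (surgical), 81–83% at 181 and about 90% at 227.

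This rests on one-sided 0.025, 1:1 allocation, the anticipated control rates, and the same rate in every stratum. The excess persists over control rates from 0.5% to 4%, and imbalance within quintiles would enlarge it. The figure of 227 is planned enrolment; the documents give no final count by arm. The consequence is confined to these two additional analyses, so the change should be made but does not touch the co-primary conclusions.

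**What to change.** For these two endpoints only:

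- Keep the n_j/n weights and replace each V_j by the variance restricted to the margin, giving a stratified Miettinen-Nurminen or Farrington-Manning score interval.
- State a two-sided 95% level (one-sided 0.025).
- State the denominator, for example all ITT subjects.
- In the synopsis, 12.1.1.2, 12.3.3 and 12.3.4, replace the 165 and 130 per arm statements with the power of that test: about 81–83% at 181 per arm and about 90% at 227, assuming arms balanced within strata and everyone in the denominator. Add that it falls to about 80–81% at 227 if treated shares run from 20 to 80% across quintiles.

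The cost is SAP wording and standard software; margins, enrolment and the co-primary analyses stay as they are. The drawbacks are a less favourable stated power and a somewhat conservative test, with an actual error of roughly 1.3–2.3% in the settings examined.
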